6.3 SUBJECT SETS ANALYSED

Treated set (TS) in monotherapy:

This patient set includes all patients enrolled in the trial who were documented to have administrated at least one dose of BI 836880 monotherapy. The TS is used for both efficacy analysis and safety analyses.

Treated set (TS) in combination therapy:

This patient set includes all patients enrolled in the trial who were documented to have administrated at least one dose of BI 836880 and ezabenlimab combination therapy. The TS is used for both efficacy analysis and safety analyses.

Dose escalation cohort treated set in monotherapy:

This patient set includes all patients enrolled in dose escalation cohort of monotherapy who were documented to have administrated at least one dose of study medication and were evaluable for the MTD determination. This set is used for dose finding and MTD determination in Part I.

Dose escalation cohort treated set in combination therapy:

This patient set includes all patients enrolled in dose escalation cohort of combination therapy who were documented to have administrated at least one dose of study medication and were evaluable for the MTD determination. This set is used for dose finding and MTD determination in Part II.

PK parameter analysis set (PKS)

The PK parameter analysis set (PKS) includes all subjects from the TS who provide at least one PK parameter that is not excluded.

6.5 HANDLING OF MISSING DATA AND OUTLIERS

Missing or incomplete AE dates are imputed according to BI standards (see “Handling of missing and incomplete AE dates”) (3). Missing data and outliers of PK data are handled according to (2). Please refer to Section 7.4 of the CTP for more details. According to (2), missing biomarker data (NOS - no sample, NOR - no valid result, NOA - not analyzed) will not be imputed. Handling of data below or above the limit of quantification, e.g. the myriad panel data:

- BLQ data will be replaced by $\frac{1}{2}$ LLOQ
- ALQ data will be replaced by ULOQ, if ULOQs are available.

Otherwise, ALQ data will be excluded from the analysis.

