The pharmacokinetics (PK) and immunogenicity of BI 836880 were investigated in cynomolgus monkeys following a single intravenous (i.v.) at 3 dose levels. BI 836880 demonstrated an unexpected dose-dependent clearance and a supra-proportionally $AUC_{0-\infty}$ increase with the increase of dose. Among the nine monkeys in this study, six monkeys were anti-drug antibodies (ADA) positive post-dose at one or more of the sampling time points. No changes in pharmacokinetic parameters were observed in these animals. In the 13-week toxicity and toxicokinetics, BI 836880 exposure (maximum concentration [C_{max}] and area under the curve [$AUC]_{0-168}$) increased approximately dose proportionally from 1 to 60 mg/kg in weeks 1, 4 and 13. There was a moderate accumulation (~ 2-fold). BI 836880 is currently tested in monotherapy in 2 phase I trials.

BI 836880 monotherapy is currently tested in two phase I trials, trial 1336-0001 for every 3 week administration schedule and trial 1336-0006 for weekly administration schedule, both conducted in Europe. 29 and 18 patients received BI 836880 in trial 1336-0001 and in trial 1336-0006 respectively. Dose levels between 40 mg and 1000 mg of BI 836880 are tested. In trial 1336-0001, the dose of 720 mg was defined as MTD and recommended phase 2 dose (RP2D).

In these two trials, the most commonly reported adverse events (AEs) are hypertension, asthenia, nausea, vomiting, diarrhoea and constipation. Other relevant AEs (mode of action related) include, peripheral oedema, bleeding (epistaxis), and proteinuria. The Safety profile of BI 836880 is as expected based on its mode of action. New antihypertensive treatment or change in previous antihypertensive treatment was needed in very few patients.

An exploratory, preliminary biomarker analysis performed in these two trials has shown that systemic VEGF levels are completely blocked already at the lowest dose of 40 mg i.v., while systemic ANG2 levels were blocked dose-dependently showing complete inhibition at dosages starting at 360 mg 3-weekly or 120 mg weekly. At these dosages both, systemic VEGF and ANG2, remain below limit of quantitation even before start of next treatment.

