5. ENDPOINT(S)

This is a phase I study, containing two parts: Part I (dose escalation of BI 836880) and part II (dose escalation of BI 836880 in combination with ezabenlimab) in Japanese patients with advanced solid tumors.

The objective of part I is to determine MTD and/or RP2D and safety, tolerability, pharmacokinetics (PK) and pharmacodynamics (Pd) of BI 836880 monotherapy.

The objective of part II is to determine MTD and/or RP2D and safety, tolerability, pharmacokinetics (PK) and pharmacodynamics (Pd) of the combination therapy of BI 836880 and ezabenlimab.

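### SAP 6.5 drops above-limit biomarker values when no ULOQ is available, which biases exploratory marker summaries downward; below-limit values also need to be counted and reported as such

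*SAP*

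**What the plan says.** SAP 6.5 introduces a general rule, with one panel as its only named example: "Handling of data below or above the limit of quantification, e.g. the myriad panel data". It has three branches.

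- Below the limit: "BLQ data will be replaced by" half the LLOQ.
- Above the limit, with a ULOQ: "ALQ data will be replaced by ULOQ, if ULOQs are available".
- Above the limit, without a ULOQ: "Otherwise, ALQ data will be excluded from the analysis".

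The visible text does not say which assays lack a ULOQ, and it asks for no count of values below or above the limit.

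Protocol 1.2.1 gives exploratory, preliminary results from two earlier trials. On VEGF it says: "systemic VEGF levels are completely blocked already at the lowest dose of 40 mg i.v". It reports complete Ang2 inhibition from 360 mg every three weeks and adds: "At these dosages both, systemic VEGF and ANG2, remain below limit of quantitation even before start of next treatment". Part I lists 360 mg and 720 mg (Protocol 4.1.3), though the SMC may agree intermediate or lower doses. Part II starts at 120 mg (Protocol 4.1.2.2).

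SAP 5 names pharmacodynamics among the objectives of both parts. Protocol 5.7 describes the biomarker and pharmacodynamic measurements as exploratory. The default summary statistics in SAP 7 are N, mean, SD, minimum, quartiles, median and maximum.

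**The concern.** There are two separate issues.

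The first is the exclusion. A result above the limit is not missing: it is known to be among the highest. The rule keeps low censored values but deletes high ones when no ULOQ is available, so the resulting bias has a known direction. A marker that rises on treatment would look flatter than it is, most of all in the cohort with the largest rise. Protocol 3.1 plans cohorts of at least three patients. In a cohort of three, one excluded value removes a third of the data and turns the median into the midpoint of the two lower values.

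The second is how heavily censored low values are presented. If most on-treatment VEGF and Ang2 values fall below the limit, they are all recorded as the same constant. A change from baseline computed from that constant depends on where the patient started. Doses or parts could then appear to differ in inhibition when only their baselines differ.

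These data can matter even though they are exploratory. Protocol 4.1.2.1 says that the RP2D in trial 1336-0001 rested on safety together with PK and pharmacodynamic analysis. Protocol 2.1.1.1 lets the SMC declare an RP2D from all available data.

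**Working it through.** The plan states no figure on this point, so there is none to reproduce. The documents give no LLOQ, ULOQ, baseline level or share of ALQ values; everything below that depends on these is an assumption.

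**Exclusion of ALQ values.** Take a log-normal marker with log-SD s (assumed 0.5, 0.7 and 1.0) and exclude the top share q = 20% (assumed).

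- Geometric mean ratio = exp(−s·φ(z)/(1−q)), with z = Φ⁻¹(0.8) = 0.842 and φ(z) = 0.280. So φ(z)/0.8 = 0.350.
- Median ratio = exp(s·Φ⁻¹(0.5 × 0.8)) = exp(−0.253·s).

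| log-SD | Geometric mean ratio | Change | Median ratio | Change |
|---|---|---|---|---|
| 0.5 | 0.84 | −16% | 0.88 | −12% |
| 0.7 | 0.78 | −22% | 0.84 | −16% |
| 1.0 | 0.70 | −30% | 0.78 | −22% |

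A simulation over other assumed shares gives these falls in the geometric mean under exclusion:

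| Share ALQ | log-SD 0.5 | log-SD 1.0 |
|---|---|---|
| 5% | 5% | 10% |
| 10% | 9% | 18% |
| 20% | 16% | 30% |
| 30% | 22% | 39% |

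Keeping the values at the limit instead leaves the median unbiased in all these cases. It reduces the fall in the geometric mean to between about 1% and 17%.

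**Substitution for BLQ values.** For a patient whose on-treatment value is BLQ, recorded change = 100 × (0.5 × LLOQ/baseline − 1).

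| Baseline / LLOQ | Recorded change |
|---|---|
| 1.2 | −58% |
| 2 | −75% |
| 4 | −87.5% |
| 10 | −95% |

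Every row describes the same laboratory finding, a value below the limit. At a baseline of 5 × LLOQ the recorded change is −90%, while the true change could lie anywhere from −80% to −100%.

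**How far baseline dominates a whole cell.** In a simulation the baseline was log-normal with median 10 × LLOQ and log-SD 0.5. Values not forced to BLQ were set at 15-60% of baseline, with half the LLOQ as a floor (all assumed). R² of the log post/baseline ratio on log baseline was 1.00 with 100% BLQ, 0.35 with 90% and 0.05 with 50%.

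**The case against.** The exclusion is only a fallback. The rule first caps at the ULOQ, and the documents name no assay without one and no marker expected to exceed it, so the fallback may never be used. That limits the known size of the problem. It does not justify the rule, which discards known-high results whenever it applies.

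For BLQ values, half-LLOQ substitution already ranks them lowest, and SAP 7 already reports median and quartiles. This stands: the order is preserved, and what is missing in the visible text is mainly counts and labelling. Biomarker sections are redacted or not shown (Protocol 2.2 and 5.4, and parts of the SAP), so such counts may be planned there. The BLQ part is therefore a conditional reporting improvement.

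A reader might go further and infer that the trial's percent-inhibition results would reflect nothing but baseline, with zero SD on treatment. The documents do not support this. No percent-inhibition measure appears in the visible text. Both effects need every post-dose value in the cell to be BLQ, and the R² figures show how quickly baseline loses its hold otherwise. The BLQ expectation comes from preliminary data in earlier trials, lower Part I doses are possible, and Part II starts below the dose reported for complete Ang2 inhibition. Nothing visible places VEGF or Ang2 in the panel named in SAP 6.5, although the rule is worded generally.

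Nor does low VEGF or Ang2 bear on the ALQ exclusion; the two issues stand on separate grounds.

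**Conclusion.** The ALQ exclusion rule is wrong as written and should be changed. Wherever it applies it biases the mean, median and upper quantiles downward; the minimum is unaffected. The 16-30% and 12-22% figures illustrate the size under an assumed 20% ALQ share and an assumed log-SD of 0.5 to 1.0. They describe large samples and do not predict the result in a cohort of three.

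The BLQ point holds conditionally: for each value below the limit, any change from baseline is determined by the baseline. If the preliminary data in Protocol 1.2.1 carry over, this will apply to most on-treatment VEGF and Ang2 values at 360 and 720 mg.

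The impact is limited to exploratory biomarker summaries. The MTD and DLT endpoints do not use this rule, and SAP 6.5 refers missing data and outliers in PK to a separate manual.

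**What to change.** In SAP 6.5:

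1. Remove the exclusion of ALQ values. Where no ULOQ exists, keep each one flagged and ranked highest, for example as above the highest quantified value, and summarise by median and quartiles.
2. For each marker, dose and visit, report the number and percentage of values BLQ and ALQ.
3. Where more than half of a cell is BLQ, report the proportion BLQ in place of a mean or percent change.

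If the sections not visible here already provide the counts in item 2, a cross-reference from SAP 6.5 is enough for that item. The cost is SAP wording and table shells, with no new data. The one small loss is that heavily censored cells would show no arithmetic mean or percent change.

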6.6 BASELINE, TIME WINDOWS AND CALCULATED VISITS

Baseline values will be the measurements taken most recently prior to first administration of study drug (same dates are allowed). If not available, then the values reported at the screening visit will be considered. For lab values, not only the examination date but also time is recorded, examination time has to be taken into account when defining baseline. That is, a laboratory value on the same date as the first study drug administration is considered as baseline value if and only if the time of laboratory value is before or the same as the time of study drug administration.

Time windows and visits will be calculated to determine the planned day of tumour measurement and response status, based on the protocol-specified tumour imaging schedule. Imaging data will be displayed as screening, and then every 2 cycles i.e.: Week 6, 12, 18, 24, for the first 6 months of treatment, then every 3 cycles thereafter (Week 33, 42, 51... etc.). In order to identify whether consecutive imaging time points are missing for a given patient, a nominal time point will be assigned to each and every image. This nominal time points and windows is defined in Table 6.6:1. Images which are not older than 28 days at start of treatment will be suffice as screening images and do not need to be repeated.

Table 6.6: 1 Nominal time points and windows for imaging

Nominal time point (weeks from start of study medication)	Due date of scans (days)*	Window (days)
6	43	1 to \leq 64
12	85	65 to \leq 106

18	127	107 to \leq 148
24	169	149 to \leq 200
33	232	201 to \leq 263
42	295	264 to \leq 326
51	358	327 to \leq 389
Etc., 9 week interval	Etc.	Etc.

* The date of the first dose of study medication is Day 1

7. PLANNED ANALYSIS

For End-Of-Text (EoT) tables, the set of summary statistics is: N / Mean / SD / Min / Q1 (lower quartile) / Median / Q3 (upper quartile) / Max.

Tabulations of frequencies for categorical data will include all possible categories and will display the number of observations in a category as well as the percentage (%) relative to the respective treatment group (unless otherwise specified, all patients in the respective patient set whether they have non-missing values or not). Percentages will be rounded to one decimal place. The category missing will be displayed only if there are actually missing values.

For PK, [REDACTED]

For analyte concentrations, the following descriptive statistics will additionally be calculated:

Nobs	Number of observations
CV	arithmetic coefficient of variation
gMean	geometric mean
gCV	geometric coefficient of variation

For PK parameters, the following descriptive statistics will additionally be calculated:

Nobs	Number of observations
CV	arithmetic coefficient of variation
gMean	geometric mean
gCV	geometric coefficient of variation
P10	10th percentile
Q1	1st quartile
Q3	3rd quartile
P90	90th percentile

The data format for descriptive statistics of concentrations will be identical with the data format of the respective concentrations. The descriptive statistics of PK parameters will be calculated using the individual values with the number of decimal places as provided by the evaluation program. Then the individual values as well as the descriptive statistics will be reported with three significant digits in the CTR.

7.1 DEMOGRAPHIC AND OTHER BASELINE CHARACTERISTICS

Only descriptive statistics are planned for this section of the report.

7.2 CONCOMITANT DISEASES AND MEDICATION

Descriptive statistics are planned for concomitant diseases. Concomitant therapies will be displayed in listing.

7.3 TREATMENT COMPLIANCE

Only descriptive statistics are planned for this section of the report.

Compliance will be calculated for subjects having attended the visit. A subject is considered having attended the visit if the indicated visit is captured in the eCRF database. In particular, if a subject attended the visit, but is not treated at the visit, the compliance of this visit is considered as 0%.

Compliance with trial medication will be based on the drug infusion/administered eCRF data and calculated as amount of drug infused/administered divided by the amount of drug to be infused/administered expressed as a percentage, see calculations below.

“Per Visit” Compliance to trial medication will be calculated as follows:

$$\frac{(\text{Amount of drug infused/administered at Visit X(n)})}{(\text{Amount of drug planned to be infused/administered at Visit X(n)})} \times 100$$

Overall Compliance to trial medication will be calculated as mean of the “per visit” compliance.

The compliance will be based on the total volume infused in mL (eCRF data) compared to total volume prepared (eCRF data).

7.4 PRIMARY ENDPOINT

In part I and II, the primary endpoint is to assess the MTD based on the number of patients presenting DLTs during the MTD evaluation period. The primary analysis is for the determination of the MTD. The purpose of this analysis is to summarize and document the data that led to the selection of the MTD. Therefore, an overall summary of DLTs (see CTP Section 4.1.7 for the definition of DLTs) which occurred during the MTD evaluation period will be provided for each dose cohort from the dose finding cohort treated set. Patients, if any, who did not complete the MTD evaluation period for reasons other than DLT will be excluded from the analysis of the primary endpoint.

A summary of the number of patients with DLTs overall in any cycle will be also given by initial treatment and displayed in a similar format to the summary of DLTs occurring in the MTD evaluation period.

The analysis of the MTD is based on a Bayesian logistic regression model (BLRM) guided by the escalation with overdose control principle. The MTD is defined as the highest dose for a given schedule that is expected to cause less than 25% risk of the true DLT rate being above or equal to 33% during the MTD evaluation period. Estimation of the MTD during the dose escalation phase of the study will be based upon the estimation of the posterior probability of the incidence of DLT in toxicity categories during the MTD evaluation period for all evaluable patients. The model to be used is specified in CTP Section 7.

The posterior probabilities that the toxicity rates of each dose level fall into the categories specified in CTP Section 7 will be displayed.

[figure not shown]
7.5 SECONDARY ENDPOINTS

7.5.1 Key secondary endpoint

This section is not applicable as no key secondary endpoint has been specified in the CTP.

7.5.2 Secondary endpoints

The analysis of standard PK parameters will be performed according to (2) and (4). In general, all dose levels from Part I and Part II will be analysed separately.

7.7 EXTENT OF EXPOSURE

Treatment exposure will be primarily summarized by the total treatment exposure time and has been defined in [Section 5.4](#) of this TSAP.

Treatment interruptions before permanent discontinuation will not be excluded. In part I, summary statistics for treatment time by each dose level, dosage of BI 836880 overtime and total treatment cycles initiated will also be provided. In part II, summary statistics for treatment time by each combination dose level, dosage of BI 836880 and ezabenlimab overtime and total treatment cycles initiated will also be provided. Dose reduction will be summarized by each dose levels from Part I and Part II separately. The maximum treatment delay in days will be summarized by each dose level for both parts.

7.8 SAFETY ANALYSIS

All safety analysis will be performed on the treated set.

7.8.1 Adverse events

The analyses of adverse events (AE) will be descriptive in nature. All analyses of AEs will be based on the number of patients with AEs and not on the number of AEs. Two analyses will be performed in part I and part II, respectively. The first analysis of safety will be performed for the first cycle of the trial (determination of the MTD, first cycle only, dose level = initial dose at the start of the treatment, dose escalation cohort treated set). This descriptive analysis will evaluate the MTD. The second analysis will be performed with respect to all cycles and will act as a support for the determination of the MTD (treated set).

For analysis of duration, severity etc. of multiple AE occurrences, data on the case report form (CRF) will be collapsed into AE episodes provided that all of the following applies:

- The same MedDRA lowest level term was reported for the occurrences.
- The occurrences were time-overlapping or time-adjacent (time-adjacency of two occurrences is given if the second occurrence started on the same day or on the day after the end of the first occurrence).
- Treatment did not change between the onset of the occurrences or treatment changed between the onsets of the occurrences, but no deterioration was observed for the later occurrence.

For further details on summarization of AE data, please refer to the guideline 'Analysis and Presentation of Adverse Event Data from Clinical Trials' ([5](#)).

For patients treated with the test drug, that means that all adverse events occurring between first drug infusion and 42 days after last drug infusion or death, whichever occurs first, will be assigned to the on-treatment period. All adverse events occurring before any study drug infusion will be assigned to 'screening' and all adverse events occurring after last study drug infusion + 42 days will be assigned to 'post-study' (for listings only). For details on the treatment definition, see [Section 6.1](#).

An overall summary of adverse events will be presented. This summary will exclude the rows 'Severe AEs', 'Significant AEs', 'AEs of special interest' and 'Other significant AEs' but will include additional rows for 'AEs leading to dose reduction' and 'AEs by highest Common Terminology Criteria (CTC) grade'.

The frequency of patients with adverse events will be summarized by highest CTC grade (grades 1, 2, 3, 4, 5 and all grades), treatment, primary system organ class and preferred term for each of the following AE tables as well as relatedness of AEs to treatment and seriousness:

For Part I and Part II:

- All AEs
- Drug-related AEs
- AEs leading to dose reduction
- Drug-related AE leading to dose reduction
- AEs leading to treatment discontinuation
- Drug-related AEs leading to treatment discontinuation
- Drug-related AEs leading to treatment discontinuation or dose reduction

- AEs leading to death
- Serious AEs
- Drug-related serious AEs
- Non-serious AE with higher than 5% occurrence rate
- Adverse Events of Special Interest (AESIs)
- DLTs

Part II only:

- Immune-related AEs
- Immune-related AEs leading to dose reduction
- Immune-related AEs leading to treatment discontinuation
- Immune-related AEs leading to treatment discontinuation or dose reduction

All tables will be sorted by system organ classes (SOC) according to the standard sort order specified by the European Medicines Agency (EMA). Preferred terms (PTs) will be sorted by frequency (within SOC).

The above tables will be repeated with the project defined grouping of AE terms. Details of the project defined groupings are defined in the technical TSAP. In these tables the grouped AEs will replace the original PTs for all AEs that are included within the grouped term. The grouped AE categories will then be tabulated along with all remaining MedDRA PTs, sorted by descending frequency.

A reference table presenting the entire project defined groupings and MedDRA PTs within each grouping will also be produced.

Additional AE tables will be produced for AEs of special interest (hepatic injury as defined in CTP Section 5.2.9.1.4 and dose limiting toxicities as defined by 4.1.7), providing further details on highest CTC grade, action taken with study drug and time to first onset of AE.

